### **Study and Site Closure**

Amgen or its designee may stop the study or study site participation in the study for medical, safety, regulatory, administrative, or other reasons consistent with applicable laws, regulations, and GCP.

Both Amgen and the Investigator reserve the right to terminate the Investigator's participation in the study according to the Clinical Trial Agreement. The investigator is to notify the IRB/IEC in writing of the study's completion or early termination and send a copy of the notification to Amgen.

Subjects may be eligible for continued treatment with Amgen investigational product(s) by an extension protocol or as provided for by the local country's regulatory mechanism. However, Amgen reserves the unilateral right, at its sole discretion, to determine whether to supply Amgen investigational product(s) and by what mechanism, after termination of the study and before the product(s) is/are available commercially.

### **Compensation**

Any arrangements for compensation to subjects for injury or illness that arises in the study are described in the Compensation for Injury section of the Informed Consent that is available as a separate document.

## Appendix 4. Safety Events: Definitions and Procedures for Recording, Evaluating, Follow-up and Reporting

Disease-related Event Definition

• Disease-related events are events (serious or non-serious) anticipated to occur in the study population due to the underlying disease. See Section 9.2.3.1.1.1 for the list of disease-related events.

• Disease-related events that would qualify as an adverse event or serious adverse event:

○ An event based on the underlying disease that is worse than expected as assessed by the investigator for the subject's condition or if the investigator believes there is a causal relationship between the investigational product(s)/study treatment/protocol-required therapies and disease worsening, this must be reported as an adverse event or serious adverse event.

• Disease-related events that do not qualify as adverse events or serious adverse events:

○ An event which is part of the normal course of disease under study (eg, disease progression in oncology or hospitalization due to disease progression) is to be reported as a disease-related event.

### Definition of Adverse Event

Adverse Event Definition

• An adverse event is any untoward medical occurrence in a clinical study subject irrespective of a causal relationship with the study treatment.

• Note: An adverse event can therefore be any unfavorable and unintended sign (including an abnormal laboratory finding), symptom, or disease (new or exacerbated) temporally associated with the use of a treatment, combination product, medical device or procedure.

Events Meeting the Adverse Event Definition

• Any abnormal laboratory test results (hematology, clinical chemistry, or urinalysis) or other safety assessments (eg, electrocardiogram [ECG], radiological scans, vital signs measurements), including those that worsen from baseline, that are considered clinically significant in the medical and scientific judgment of the investigator (ie, not related to progression of underlying disease).

• Exacerbation of a chronic or intermittent pre-existing condition including either an increase in frequency and/or intensity of the condition.

• New conditions detected or diagnosed after study treatment administration even though it may have been present before the start of the study.

• Signs, symptoms, or the clinical sequelae of a suspected drug-drug interaction.

• Signs, symptoms, or the clinical sequelae of a suspected overdose of either study treatment or a concomitant medication. Overdose per se will not be reported as an

adverse event/serious adverse event unless it is an intentional overdose taken with possible suicidal/self-harming intent. Such overdoses are to be reported regardless of sequelae.

- “Lack of efficacy” or “failure of expected pharmacological action” per se will not be reported as an adverse event or serious adverse event. Such instances will be captured in the efficacy assessments. However, the signs, symptoms, and/or clinical sequelae resulting from lack of efficacy will be reported as adverse event or serious adverse event if they fulfill the definition of an adverse event or serious adverse event.

OR

- The signs, symptoms, and/or clinical sequelae resulting from lack of efficacy will be reported as adverse event or serious adverse event if they fulfill the definition of an adverse event or serious adverse event. Also, “lack of efficacy” or “failure of expected pharmacological action” also constitutes an adverse event or serious adverse event.

#### Events NOT Meeting the Adverse Event Definition

- Medical or surgical procedure (eg, endoscopy, appendectomy): the condition that leads to the procedure is the adverse event.
- Situations in which an untoward medical occurrence did not occur (social and/or convenience admission to a hospital).
- Anticipated day-to-day fluctuations of pre-existing disease(s) or condition(s) present or detected at the start of the study that do not worsen.

#### Definition of Serious Adverse Event

**A Serious Adverse Event is defined as any untoward medical occurrence that, meets at least 1 of the following serious criteria:**

- **Results in death (fatal)**
- **Immediately life-threatening**

The term “life-threatening” in the definition of “serious” refers to an event in which the subject was at risk of death at the time of the event. It does not refer to an event, which hypothetically might have caused death, if it were more severe.

- **Requires in-patient hospitalization or prolongation of existing hospitalization**

In general, hospitalization signifies that the subject has been detained (usually involving at least an overnight stay) at the hospital or emergency ward for observation and/or treatment that would not have been appropriate in the physician’s office or outpatient setting. Complications that occur during hospitalization are an adverse event. If a complication prolongs hospitalization or fulfills any other serious criteria,

the event is serious. When in doubt as to whether "hospitalization" occurred or was necessary, the adverse event is to be considered serious.

Hospitalization for elective treatment of a pre-existing condition that did not worsen from baseline is not considered an adverse event.

**• Results in persistent or significant disability/incapacity**

The term disability means a substantial disruption of a person's ability to conduct normal life functions.

This definition is not intended to include experiences of relatively minor medical significance such as uncomplicated headache, nausea, vomiting, diarrhea, influenza, and accidental trauma (eg, sprained ankle) which may interfere with or prevent everyday life functions but do not constitute a substantial disruption.

**• Is a congenital anomaly/birth defect**

**• Other medically important serious event**

Medical or scientific judgment is to be exercised in deciding whether serious adverse event reporting is appropriate in other situations such as important medical events that may not be immediately life-threatening or result in death or hospitalization but may jeopardize the subject or may require medical or surgical intervention to prevent 1 of the other outcomes listed in the above definition. These events are typically to be considered serious.

Examples of such events include invasive or malignant cancers, intensive treatment in an emergency room or at home for allergic bronchospasm, blood dyscrasias or convulsions that do not result in hospitalization, or development of drug dependency or drug abuse.

### **Definition of Adverse Device Effect**

The detection and documentation procedures for adverse device effects described in this protocol apply to all medical devices provided for use in the study (see [Section 7.1.3](#) for the list of medical devices).

### Adverse Device Effect Definition

An adverse device effect is any adverse event related to the use of a combination product or medical device. Adverse device effects include adverse events resulting from insufficient or inadequate instructions for use, adverse events resulting from any malfunction of the device, or adverse events resulting from use error or from intentional misuse of the device.

### Recording Adverse Events, Disease-related Events (if applicable), and Serious Adverse Events

#### Adverse Event, Disease-related Event (if applicable) and Serious Adverse Event Recording

- If the severity of an adverse event changes from the date of onset to the date of resolution, record as a single event with the worst severity on the Event CRF
- When an adverse event, disease-related event or serious adverse event occurs, it is the responsibility of the investigator to review all documentation (eg, hospital progress notes, laboratory, and diagnostics reports) related to the event.
- The investigator will then record all relevant adverse event/disease-related event/serious adverse event information in the Event case report form (CRF).
  - Additionally, the investigator is required to report a fatal disease-related event on the Event CRF.
- The investigator must assign the following adverse event attributes:
  - Adverse event diagnosis or syndrome(s), if known (if not known, signs or symptoms);
  - Dates of onset and resolution (if resolved);
  - Severity (or toxicity defined below);
  - Assessment of relatedness to investigational product, or devices; and
  - Action taken.
- It is not acceptable for the investigator to send photocopies of the subject's medical records to sponsor in lieu of completion of the Event CRF page.
- If specifically requested, the investigator may need to provide additional follow-up information, such as discharge summaries, medical records, or extracts from the medical records. In this case, all subject identifiers, with the exception of the subject number, will be blinded on the copies of the medical records before submission to the sponsor.
- The investigator will attempt to establish a diagnosis of the event based on signs, symptoms, and/or other clinical information. In such cases, the diagnosis (not the individual signs/symptoms) will be documented as the adverse event/serious adverse event.

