#### **9.2.3.1.1.3 Serious Adverse Events**

The investigator is responsible for ensuring that all serious adverse events observed by the investigator or reported by the subject that occur after signing of the informed consent through the end of the safety follow-up visit (18 weeks after last dose of investigational product or EOS) are reported using the Event CRF.

All serious adverse events will be collected, recorded and reported to the sponsor or designee within 24 hours, as indicated in [Appendix 4](#). The investigator will submit any updated serious adverse event data to the sponsor within 24 hours of it being available.

The criteria for grade 4 in the CTCAE grading scale differs from the regulatory criteria for serious adverse events. It is left to the investigator's judgment to report these grade 4 abnormalities as serious adverse events.

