### Follow-up of Adverse Event and Serious Adverse Event

- The investigator is obligated to perform or arrange for the conduct of supplemental measurements and/or evaluations as medically indicated or as requested to elucidate the nature and/or causality of the adverse event or serious adverse event as fully as possible. This may include additional laboratory tests or investigations, histopathological examinations, or consultation with other health care professionals.
- If a subject is permanently withdrawn from protocol-required therapies because of a serious adverse event, this information must be submitted to Amgen.
- New or updated information will be recorded in the originally completed Event CRF.
- The investigator will submit any updated serious adverse event data to Amgen within 24 hours of receipt of the information.

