#### **3. Serious Adverse Event**

Provide the date the Investigator became aware of this Information

Serious Adverse Event Diagnosis or Syndrome\* –

- If the diagnosis is known, it should be entered. Do not list all signs/symptoms if they are included in the diagnosis.
- If a diagnosis is not known, the relevant signs/symptoms should be entered.
- If the event is fatal, the cause of death should be entered and autopsy results should be submitted, when available.

Date Started\* – Enter date the adverse event first started (not the date on which the event met serious criteria) rather than the date of diagnosis or hospitalization. This is a mandatory field.

Date Ended – Enter date the adverse event ended and not the date when the event no longer met serious criteria. If the event has not ended at the time of the initial report, a follow-up report should be completed when the end date is known. If the event is fatal, enter the date of death as the end date.

If event occurred before the first dose of Investigational Product (IP)/drug under study, add a check mark in the corresponding box.

Is event serious?\* – Indicate Yes or No. This is a mandatory field.

Serious Criteria Code\* – This is a mandatory field for serious events. Enter all reasons why the reported event has met serious criteria:

- Immediately life-threatening – Use only if the subject was at immediate risk of death from the event as it occurred. Emergency treatment is often required to sustain life in this situation.
- If the investigator decides an event should be reported in an expedited manner, but it does not meet other serious criteria, "Other Medically Important Serious Event" may be the appropriate serious criterion.

Relationship to IP – The Investigator must determine and enter the relationship of the event to the IP at the time the event is initially reported. This is a mandatory field.

Relationship to Amgen device\* – The Investigator must determine and enter the relationship of the event to the Amgen device (e.g. prefilled syringe, auto-injector) at the time the event is initially reported. If the study involves an Amgen device, this is a mandatory field. This question does not apply to non-Amgen devices used in the study (e.g. heating pads, infusion pumps)

Outcome of Event\* – Enter the code for the outcome of the event at the time the form is completed. This is a mandatory field.

- Resolved – End date is known
- Not resolved / Unknown – End date is unknown

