5.1.2 Safety Endpoints

Treatment-emergent Adverse Event (TEAE)

An adverse Event (AE) recorded on the Events eCRF page that occurs on or after the date of the first dose of investigational product (IP), as determined by the flag indicating the event did not start before first dose of IP on the Events eCRF, and up to and including **126 days** after the end of IP (ie. **18 weeks** after the last dose of IP).

Serious TEAE

A serious treatment-emergent adverse event is an SAE considered to be treatment-emergent.

Disease-Related Event (DRE)

Disease-related Events (DREs) are events determined by the flag on the Event CRF.

Columbia-Suicide Severity Rating Scale (C-SSRS)

The C-SSRS is a clinician rating of suicidal behavior and ideation. Two versions depending on the type of visits will be used in this study: Screening and Since Last Visit. The C-SSRS consists of a maximum of 20 items, which defines 5 subtypes of suicidal ideation and behavior in addition to self-injurious behavior with no suicidal intent. The C-SSRS will be administered by the principal investigator or qualified designee to evaluate suicidal behavior and suicidal ideation. For the baseline assessment, for measurements with multiple individual items, all individual items from the same set of measurement will be used for analysis.

For C-SSRS, the last complete assessment prior to first IP administration will be used as the baseline. If subject completes C-SSRS form on Day 1 then all individual items from Day 1 visit will be used as baseline. If subject does not complete C-SSRS form on Day 1 then all individual items from Week -4 visit will be used as baseline. Please refer to [Appendix E](#) for more information.

Beck Depression Inventory (BDI)-II

The BDI-II is a 21-item questionnaire that assesses severity of depression. Each item is scored from 0 to 3. The total score is categorized into 4 severity grades: Minimal depression (0-13), mild depression (14-19), moderate depression (20-28) and severe depression (29-63). Please refer to Appendix E for more information.

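### SAP 5.1.2 has no worsening clause, so a pre-dose SAE that worsens, or a pre-dose event that first becomes serious, on treatment may not count as treatment-emergent

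*Protocol*

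**What the plan says.** **Definition.** Under SAP 5.1.2 a TEAE occurs on or after the first dose, "as determined by the flag indicating the event did not start before first dose of IP on the Events eCRF", and no later than 126 days after the last dose. A serious TEAE is an SAE that meets that definition. Neither definition mentions a rise in grade or an event becoming serious. SAP 2.1 names the incidence of TEAEs as a secondary safety endpoint.

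**Recording.** When severity changes between an event's onset and its resolution, Protocol Appendix 4 tells the site to "record as a single event with the worst severity on the Event CRF". The attributes the investigator must assign include onset and resolution dates but no date of worsening. The follow-up rules add: "New or updated information will be recorded in the originally completed Event CRF".

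**Dating of serious events.** The completion instructions for the SAE contingency form (Appendix 4, Figure 12-1) say: "Enter date the adverse event first started (not the date on which the event met serious criteria". They also rule out dating from diagnosis or admission. They add: "If event occurred before the first dose of Investigational Product (IP)/drug under study, add a check mark in the corresponding box".

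**Collection windows.** Adverse events are collected only after the first dose (Protocol 9.2.3.1.1.2). SAEs are collected when they "occur after signing of the informed consent through the end of the safety follow-up visit" (Protocol 9.2.3.1.1.3). Screening and baseline together last up to 7 weeks (Protocol 5.3.2), or longer with the sponsor's approval (Protocol 6.6).

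**Worsening of something already present.** Appendix 4 lists among events that meet the adverse event definition: "Exacerbation of a chronic or intermittent pre-existing condition including either an increase in frequency and/or intensity of the condition". Protocol 9.2.1.3 collects a CTCAE grade for each unresolved condition in the medical history.

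**The concern.** On-treatment worsening of something already present is a standard form of drug toxicity, and a definition of treatment emergence should say how it is handled. Here the definition looks only at when the event started. The recording rules fold later changes into the existing record, and the one detailed instruction on start dates points back to the first start.

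If a site follows all three, an event that turns serious or gets worse after AMG 301 or placebo keeps a pre-dose onset and leaves the treatment-emergent comparison. A site that follows the exacerbation rule instead would enter a new post-dose event and count it. The same clinical course could then be classified differently at different sites, within an endpoint the SAP names. The single record carries the worst grade and no date of worsening, so the analysis team could not reliably separate the two parts afterwards.

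**Working it through.** The plan gives no figure to reproduce, and no sample-size or alpha calculation bears on the point. The check is to follow each type of event through the rules.

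**Step 1: can an Event CRF record exist before dosing?** For SAEs, yes: collection starts at consent. For non-serious adverse events, no: collection starts after the first dose, and an unresolved condition sits in the medical history with its grade.

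**Step 2: four cases.**

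- *(a) A non-serious condition is present before dosing and worsens on treatment without becoming serious.* No earlier adverse event record exists to merge with. Appendix 4 makes the exacerbation an adverse event. If the site dates it from the worsening, the flag is satisfied and it is a TEAE. Captured.
- *(b) An SAE begins between consent and first dose, is still ongoing, and worsens on treatment.* A record already exists. The single-record and follow-up rules keep the worsening in it, its start is pre-dose, and the flag excludes it. Not a TEAE or a serious TEAE if the site treats it as the same event.
- *(c) A non-serious event begins before dosing and first becomes serious on treatment.* The contingency-form instruction dates it from first start, so the flag excludes it. The exacerbation rule would support a new post-dose event. The documents do not settle which applies.
- *(d) Migraine or headache is worse than expected for the subject.* Protocol 9.2.3.1.1.1 and Appendix 4 move it from disease-related event to adverse event or SAE, so it can be treatment-emergent.

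The gap is therefore confined to (b) and (c), both of which concern serious events.

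**Step 3: does another rule close it?** SAP 8.3.1 imputes partial start dates using the same flag, so it does not. SAP 9.6.1 and 9.6.2 tabulate serious adverse events without expressly limiting them to treatment-emergent ones. An event in (b) or (c) may appear there, but it would still be missing from the TEAE and serious TEAE counts. If pre-dose SAEs are included, those tables also mix pre-dose and on-treatment events.

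**Step 4: size.** A count needs the number of SAEs with onset between consent and Day 1 that later worsen, plus the number of pre-dose complaints that become serious after Day 1. The documents give neither rate.

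**The case against.** The strongest reply is that the rules concern the adverse event, not the underlying condition. The single-record rule speaks of severity between an event's own onset and resolution. The contingency form puts contributing pre-existing conditions under relevant medical history and keeps them out of the event description. Read that way, a post-dose exacerbation is a new event with a post-dose start.

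This is right for case (a). A reader might infer that anything present before dosing that worsens can never be treatment-emergent. The documents do not support that: they collect non-serious adverse events only after the first dose, hold earlier conditions in medical history, and make their exacerbation an adverse event. The reply does not dispose of (b), where an SAE record already exists, and leaves (c) open, because the form expressly declines to date an event from when it became serious.

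Further points stand in part:

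- **The first-start wording is in a fallback form.** EDC is the primary route, and the general rules ask only for onset and resolution dates. The CRF instructions are not among the documents, so the EDC convention is unseen. Events reported on the form must, however, also be entered in EDC, and no other detailed start-date instruction is given.
- **The cases should be rare.** Exclusions 217, 218 and 233 let the investigator keep out subjects with unstable or clinically significant conditions. This limits the number and does not repair the rule.
- **The information is not wholly lost.** Admission and discharge dates are on the form, SAE updates are due within 24 hours, laboratory shifts and vital-sign changes are summarised regardless of the flag, and safety comparisons are descriptive. Admission dates help only for hospitalised events, and no analysis rule uses them.

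**Conclusion.** The point holds in a limited form. SAP 5.1.2 has no worsening clause. With the single worst-severity record and first-start dating, an SAE that began before the first dose and worsens, or a pre-dose event that first becomes serious on treatment, may not be counted as a TEAE or serious TEAE. This conflicts with the rule that exacerbation of a pre-existing condition is an adverse event.

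The conclusion assumes that sites treat the worsening as the same event and that the EDC flag follows the same first-start convention as the contingency form.

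The number affected cannot be computed and is likely very small. A reader might try an estimate: if 2% to 3% of 335 subjects had an SAE (6.7 to 10.1) and 10% to 40% of those were worsening of something already present, the result would be 0.7 to 4.0 subjects. The documents support neither factor, and the second includes worsening of medical-history conditions that the exacerbation rule already captures, so the range is not an estimate of this gap and is probably too high. The change is still worth making, because a stated rule can misclassify on-treatment serious worsening within a named endpoint.

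**What to change.** **SAP 5.1.2.** Define a TEAE as an event that starts on or after the first dose, or one that started before it and increases in CTCAE grade or becomes serious on or after it, within the existing follow-up limit. The serious TEAE definition then follows.

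**Protocol Appendix 4 (recording rules and Figure 12-1 instructions) and the CRF instructions.** State that post-dose worsening of a condition or event present before the first dose is recorded as a separate event, with onset at the date of worsening. Keep the single-record rule for events that start after the first dose. The SAP clause needs this companion because a single record holds no date of worsening.

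With both changes, the exacerbation rule, the single-record rule, the start-date instruction and the TEAE flag agree. The cost is a short clause in the SAP and a short addition to Appendix 4 and the CRF instructions, with no effect on design or treatment. The downside is a few more TEAEs reported in all arms. SAP 5.6 already counts a subject once for repeated occurrences of the same event, which limits double counting.
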